- The time to achieving treatment-emergent ADA_b positivity, separated by treatment group and defined subcategory, will be analyzed based on Kaplan-Meier methods. **This will be shown only for Categories 2 and 8 above.** Participants will be considered to have an event at the time point at which treatment emergent ADA_b positive is first achieved (taking the MSR into consideration for sub-category 5). Participants classified as treatment-emergent ADA_b negative will be censored at the time of the last available ADA_b result.
- A summary of HiSCR₅₀ responders at Week 16, separated by treatment group, as a function of ADA_b titer will be presented graphically. ~~This will be repeated for HiSCR₇₅ responders.~~
- Individual plots of plasma bimekizumab concentrations/ ADA_b titer both plotted on the Y-axes by visit (x-axis) for the full treatment period (excluding SFU for interim analyses and including SFU for final analyses) will be presented for participants with and without HiSCR₅₀ response at Week 16.
- Spaghetti plots of ADA_b titer (y-axis) by visit (x-axis), separated by treatment group for all ADA_b positive participants, including Baseline positive participants.
- Box plots of ADA_b titer (logscale) by time to first ADA_b positivity by treatment group.

~~For purposes of efficacy subgroup analyses based on anti bimekizumab antibody status, 2 categories will be used:~~

- ~~ADA_b positive~~ This is defined as participants who have ADA_b levels above the specified cut point on at least 2 time points while on treatment (ie, excluding Baseline, excluding SFU).
- ~~ADA_b negative~~ Participants who are not defined as anti bimekizumab positive (as described above) will be defined as ADA_b negative.

The groups for defining ADA_b status for safety subgroup analyses are as follows:

- AEs starting before first ADA_b positive result
- AEs starting on or after first ADA_b positive result
- AEs for participants who were always ADA_b negative

This is further explained in Section 10.2.2.

Change #35

The following section was added:

COVID-19 related considerations (Section 10.2.1.1)

To assess the impact of COVID-19 mass vaccination on TEAEs, a sensitivity analysis will present all TEAEs excluding TEAEs assessed as exclusively related to COVID-19 vaccine by the investigator. TEAEs recorded as related to both study medication and COVID-19 vaccination should not be excluded. A complementary table and listing of TEAEs related to COVID-19 vaccine will be presented.

Another sensitivity analysis will present all TEAEs excluding TEAEs with start date on or up to 5 days after date of COVID-19 vaccine. Note that study participants may receive more than one

administration of COVID-19 vaccine. A complementary table and listing of TEAEs with start date on or up to 5 days after date of COVID-19 vaccine will also be presented.

Change #36

Section 10.2.2 AE summaries

The following AE summaries were added:

- Incidence of TEAEs Excluding TEAEs Exclusively Related to COVID-19 Vaccine by SOC, HLT, and PT
- Incidence of TEAEs Exclusively Related to COVID-19 Vaccine by SOC, HLT, and PT
- Incidence of COVID-19 Vaccine Interval Censored TEAEs by SOC, HLT, and PT
- Incidence of COVID-19 Vaccine Interval TEAEs by SOC, HLT, and PT

Change #37

Section 10.2.2 AE summaries

The following text was added:

The following table will be presented for the combined Initial and Maintenance Treatment Period. **This summary will include only AEs that occur while a participant is on bimekizumab. Any AEs in the Initial Treatment Period that begin while a participant is on placebo will be excluded.**

- Incidence of TEAEs per 100 subject years by SOC, HLT, and PT and by Time of Onset Relative to Anti-bimekizumab Antibody Status. **This will include columns for the following:**
 - **TEAEs starting before the first ADAb positive result (includes ADAb categories 2 and 5) where TEAEs have occurred before the following events: a) the first positive ADAb result for subjects in category 2 and b) the first post-Baseline boosted ADAb titer result for subjects with titer results and the first post-Baseline positive ADAb result for subjects with positive ADAb at Baseline with no other samples with titer available for subjects in category 5**
 - **TEAEs starting on the same date or after the first ADAb positive result (includes ADAb Categories 2, 3, 4, 5 and 6) where TEAEs have occurred on or after the following events: a) the first positive ADAb results for subjects in categories 2, 3, 4 and 6, and b) the first post-Baseline boosted ADAb titer result for subjects with titer results and the first post-Baseline positive ADAb result for subjects with positive ADAb at Baseline with no other samples with titer available for subjects in category 5**
 - **TEAEs for subjects who are ADAb negative at all timepoints (includes ADAb Category 1)**

The tables with risk differences will also be accompanied by figures (dot plots) which show the incidence of the adverse events and corresponding 95% risk difference confidence intervals. These will be ordered by descending order of risk difference (bimekizumab vs placebo).

Change #38

Section 10.2.3.3 Major adverse cardiac event

The entire section was updated:

Potential cardiovascular events are adjudicated by the independent Cardiovascular Event Adjudication Committee (CV-CAC) according to the CV-CAC Charter (version 6.0). Adjudicated events are classified by the CV-CAC to one of the event types as defined in [Table 10–1](#). The classification of an event as a Major Adverse Cardiac Event (MACE) is also determined by the CV-CAC. Events which are classified by the CV-CAC as any of the event types identified in the third column of [Table 10–1](#) will be considered an extended MACE. Note that extended MACE is determined programmatically and includes a broader scope definition of MACE.

MACE as determined by the CV-CAC will be presented in a table and listing. Extended MACE will be presented separately in a table and listing.

Another table and listing will present the adjudicated cardiovascular events by type. For each cardiovascular event type, the individual PTs which fall within each event type will be summarized. This listing will indicate whether each event was determined to be a MACE and/or an extended MACE.

Additionally, a listing of all events identified for potential review by the CV-CAC will be produced. This listing will indicate whether each event was identified by the CV-CAC Chair for full committee review.

Table 13–1: Cardiovascular event classifications

Event Type Code	Event Type	Extended MACE
1	Non-Fatal Myocardial Infarction (MI)	Yes
2	Non-Fatal Stroke: hemorrhagic	Yes
3	Non-Fatal Stroke: ischemic	Yes
4	Non-Fatal Stroke: embolic	Yes
5	Non-Fatal Stroke: undeterminable	Yes
6	Hospitalization or ER for Unstable Angina with urgent revascularization	Yes
7	Hospitalization or ER for Unstable Angina without urgent revascularization	No
8	Hospitalization for Heart Failure	Yes
9	Transient Ischemic Attack (TIA)	No
10	Coronary Revascularization Procedures (e.g. percutaneous coronary intervention, coronary artery bypass grafting)	Yes

Table 13–1: Cardiovascular event classifications

Event Type Code	Event Type	Extended MACE
11	Urgent Revascularization Procedures (i.e. due to symptoms of brain ischemia or pending infarction)	Yes
12	Arrhythmia (not associated with ischemia)	No
13	Peripheral Arterial Event	No
14	Venous Thromboembolic Event: pulmonary embolism (PE)	No
15	Venous Thromboembolic Event: deep vein thrombosis (DVT)	No
16	Venous Thromboembolic Event: PE and DVT	No
17	Other CV Event	No
18	Death due to Myocardial Infarction (MI)	Yes
19	Death due to Stroke	Yes
20	Sudden Cardiac Death	Yes
21	Other CV Death (e.g. heart failure, pulmonary embolism, cardiovascular procedure-related)	Yes
22	Cardiovascular: Undetermined Cause of Death (i.e. cause of death unknown)	Yes
23	Non-Cardiovascular Death	No
24	Non-Cardiovascular Event	No
99	Inadequate information to adjudicate	No

CV=Cardiovascular; DVT=Deep Vein Thrombosis; ER=Emergency Room; MACE= Major Adverse Cardiac Event; MI=Myocardial Infarction; PE=Pulmonary Embolism; TIA=Transient Ischemic Attack.

MACE is determined by the adjudication committee and is not identified programmatically based on event type.

Change #39

Section 10.2.3.5 Suicidal Ideation and Behavior

The entire section was updated:

Potential neuropsychiatric events are adjudicated by the independent Neuropsychiatric Adjudication Committee according to the Neuropsychiatric Adjudication Committee (version 8.0). Adjudicated events are classified by the Committee as Suicidal or Non-suicidal. Adjudicated events are also further classified by the Committee to one of the event types as

defined in [Table 10–2](#). Suicidal Ideation and Behavior (SIB) is defined as events classified by the Committee as Suicidal.

A table and listing will present SIB events.

Another table and listing will present the adjudicated neuropsychiatric events by type. For each neuropsychiatric event type, the individual PTs which fall within each event type will be summarized. This listing will indicate whether each event was determined to be Suicidal or Non-Suicidal. For event type suicidal ideation, the listing will also indicate if intent was present and if the suicidal ideation was clinically significant.

Additionally, a listing of all events identified for potential review by the Committee will be produced. This listing will indicate whether each event was identified by the Neuropsychiatric Event Adjudication Committee Chair for full committee review.

Table 13–2: Neuropsychiatric event classifications

Event Type Code	Event Classification	Event Type
1	Suicidal	Suicidal events/completed suicide
2	Suicidal	Suicide attempt
3	Suicidal	Preparatory acts toward imminent suicidal behavior
4	Suicidal/Non-suicidal ^a	Suicidal ideation
7	Non-suicidal	Nonsuicidal Self-injurious behavior
8	Non-suicidal	Nonsuicidal Other
99	Not applicable	Inadequate information to adjudicate

^a Suicidal ideation event types can be classified by the Neuropsychiatric Adjudication Committee as Suicidal or Non-suicidal depending on whether intent to die was present.

Change #40

Section 10.2.3.6 Inflammatory bowel disease

The entire section was updated:

Selected gastrointestinal events are adjudicated by the independent Inflammatory Bowel Disease (IBD) Adjudication Committee (IBD-CAC) according to the IBD-CAC Charter (version 3.0). Adjudicated events are classified by the IBD-CAC into one of the diagnostic types as defined in [Table 10–3](#). The events will further be classified as definite, probable or possible IBD.

An overview of adjudicated IBD events will be stratified by subjects with or without a previous medical history of IBD. Previous medical history of IBD will be determined using the information recorded on the History of IBD CRF page ("Does subject have a history of IBD?"). This overview table will present events adjudicated by the IBD-CAC as either possible, probable or definite IBD. Definite and probable IBD will also be aggregated and summarized in this table.

In addition, this table will summarize each IBD event classification (possible, probable or definite) separately.

Another table and listing will present the adjudicated IBD events by type. For each IBD event type, the individual PTs which fall within each event type will be summarized.

Additionally, a listing of all events identified for potential review by the IBD-CAC will be produced. This listing will indicate whether each event was identified by the IBD-CAC Chair for full committee review.

A further supportive listing will present the individual diagnostic criteria met for each adjudicated IBD event.

Table 13–3: IBD event classifications

Event Type Code	Event Type (Classification and diagnosis)	Classification
1	Possible Inflammatory Bowel Disease – Crohn’s Disease	Possible
2	Probable Inflammatory Bowel Disease – Crohn’s Disease	Probable
3	Definite Inflammatory Bowel Disease – Crohn’s Disease	Definite
4	Possible Inflammatory Bowel Disease – Ulcerative Colitis	Possible
5	Probable Inflammatory Bowel Disease – Ulcerative Colitis	Probable
6	Definite Inflammatory Bowel Disease – Ulcerative Colitis	Definite
7	Possible Inflammatory Bowel Disease – type unclassified	Possible
8	Probable Inflammatory Bowel Disease – type unclassified	Probable
9	Definite Inflammatory Bowel Disease – type unclassified	Definite
10	Symptoms not consistent with Inflammatory Bowel Disease	Not applicable
11	Possible Inflammatory Bowel Disease – Microscopic Colitis	Possible
12	Probable Inflammatory Bowel Disease – Microscopic Colitis	Probable
13	Definite Inflammatory Bowel Disease – Microscopic Colitis	Definite
14	Possible Inflammatory Bowel Disease – no further differentiation possible	Possible
15	Probable Inflammatory Bowel Disease – no further differentiation possible	Probable
16	Definite Inflammatory Bowel Disease – no further differentiation possible	Definite
99	Not enough information to adjudicate	Not applicable

IBD=inflammatory bowel disease.

Note: IBD diagnoses of “microscopic colitis” and “no further differentiation possible” were added in an adjudication charter amendment, accounting for the event type numbering.

Change #41

Section 10.2.3.8 Hepatic events and PDILI

The following word was added:

Cases of **potential** Hy's Law will be reported separately in a liver function test table.

Change #42

Section 12.1 Appendix A: MedDRA algorithmic approach to anaphylaxis

The following text was added:

- An **algorithmic approach** which combines a number of anaphylactic reaction symptoms in order to increase specificity. A case must include one of the following where both occur on either the same day as when an injection was administered or one day after, and for scenarios where two events must have been reported, both events must have occurred within one day of each other (**as anaphylaxis is an acute event, imputed dates should not be used in the algorithmic approach**):

PUBLIC COPY
This document cannot be used to support any marketing authorization application and any extensions or variations thereof.

STATISTICAL ANALYSIS PLAN SIGNATURE PAGE

This document has been reviewed and approved per the Review and Approval of Clinical Documents Standard Operating Procedures. Signatures indicate that the final version of the Statistical Analysis Plan (SAP) or amended SAP is released for execution.

PUBLIC COPY
This document cannot be used to support any marketing authorization application and any extensions or variations thereof.

Approval Signatures

Name: hs0004-sap-amend-2
Version: 2. 0
Document Number: CLIN-000188631
Title: HS0004 SAP Amendment 2
Approved Date: 07 Jul 2022

Document Approvals	

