9.3.2 Anti-bimekizumab antibodies

Anti-bimekizumab antibodies (ADAb) will be measured using a 3-tiered assay approach: screening assay, confirmatory assay, and titration assay. Samples confirmed as positive within the confirmatory assay will be further evaluated for the presence of neutralizing anti-bimekizumab antibodies specific to IL-17AA, IL-17FF or both. Samples will be taken at Baseline, then at study Weeks 4, 8, 12, 16, 20, 24, 36 and 48, and at PEOT and SFU timepoints.

ADAb samples are not analyzed when study participants are on a treatment other than bimekizumab. For study participants who switch from placebo to bimekizumab, samples are analyzed starting at the visit when the switch to bimekizumab occurs (Week 16). The sample at Week 16 will act as the Baseline for that treatment group.

The screening cut point will be used to determine the status of anti-bimekizumab antibodies in the test sample as Positive Screen (PS) or Negative Screen (NS). For samples presenting anti-bimekizumab antibody levels that are PS, a further confirmatory assay will be performed, and the result of which will be reported as either Positive Immunodepletion (PI) or Negative Immunodepletion (NI).

ADAb status for each sample will be derived as follows:

- Sample values that are either NS, or PS and NI and where the bimekizumab concentration is less than the validated ADAb assay drug tolerance limit will be defined as anti-bimekizumab antibody negative.
- Sample values that are either NS, or PS and NI and where the bimekizumab concentration exceeds the validated ADAb assay drug tolerance limit will be defined as inconclusive.

- Sample values that are PS and PI will be defined as ADAb positive (regardless of availability of a titer value)
- Missing or non-evaluable samples will be defined as missing

Positive immunodepletion samples will be titrated, and the ADAb titer (reciprocal dilution factor including minimum required dilution) will be reported. Subsequently, PI samples will also be subject to a neutralizing assay to evaluate the potential of ADAb to neutralize the target binding of bimekizumab (IL-17AA or IL-17FF or both) in vitro.

Cumulative ADAb status will be derived as follows:

The ADAb status (positive, negative or missing) will be considered in a cumulative manner at each time point.

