A study participant will be counted positive from the first visit at which the study participant achieved a positive ADAb sample result to the end of the treatment period, regardless of any missing/inconclusive or negative ADAb sample result.

If a study participant has only negative ADAb samples or only one missing/inconclusive sample with all other ADAb samples being negative, the study participant will be classified as negative. An exception remains for the Baseline Visit where only one sample could be available. If the sample is missing/inconclusive, then the sample will be classified as being negative for the cumulative ADAb status.

Otherwise, the study participant will be classified in the missing ADAb category.

Overall ADAb status will be derived as follows:

A study participant will be classified as:

- Positive if the study participant has at least one positive sample up to the time point of interest (regardless of having missing/inconclusive data).
- Negative if the study participant has all the samples negative or only one missing/inconclusive sample with negative ADAb samples up to the timepoint of interest.
- Missing if the study participant has more than one missing ADAb result (or have more than one inconclusive sample) and all other available ADAb samples are negative up to the time point of interest.

ADAb categories will be derived as follows:

- **Pre ADAb negative – treatment-emergent ADAb negative (Category 1):** Includes study participants who are anti-bimekizumab antibody negative at Baseline and anti-bimekizumab antibody negative at all sampling points during the period of interest (one post-Baseline missing/inconclusive sample is allowed for subjects with pre- anti-bimekizumab antibody negative sample). This group also includes study participants who have a missing or inconclusive sample (either missing or inconclusive or insufficient volume) at Baseline (ie, pre-treatment) with all post-Baseline samples as ADAb negative.
- **Pre ADAb negative – treatment-emergent ADAb positive (Category 2):** Includes study participants who are ADAb negative at Baseline and ADAb positive at any sampling points post-Baseline during the period of interest. This group also includes study participants who

have a missing sample (either missing or insufficient volume) at Baseline (ie, pre-treatment) with 1 or more post-Baseline samples as ADA_b positive.

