- **Missing:** Includes study participants who are ADA_b negative, missing, or inconclusive at Baseline with some post-Baseline samples as missing or inconclusive, and other samples as ADA_b negative.

For purposes of efficacy subgroup analyses based on anti-bimekizumab antibody status, the following categories can also be used:

- ADA_b positive – This is defined as study participants who are anti-bimekizumab antibody positive on at least 2 time points while on treatment (ie, excluding Baseline, excluding SFU).
- ADA_b negative – Study participants for who either:

- All samples (including Baseline) are ADAb negative and there are no missing or inconclusive samples
- Only 1 sample is ADAb positive and all other samples (including Baseline) are ADAb negative or missing or inconclusive
- Only 1 sample is missing or inconclusive and the remaining ADAb samples are negative.
- ADAb missing - Defined as study participants who do not fulfil the criteria for one of the 2 groups listed above.

The rationale for requiring at least 2 time points in which ADAb levels are above the specified cut point is to exclude those study participants who have only one occurrence of ADAb levels during the course of treatment. Including such study participants would increase the number of ADAb positive study participants with potentially no impact on efficacy.

In the case that a sample is collected 1 or more days following the scheduled visit date in which the drug was administered, the ADAb results for that sample will be associated with the scheduled visit and summarized accordingly. Such samples will also be considered when ADAb results are summarized over a given study period.

Analysis

Immunogenicity will be assessed through summary tables and figures, and listing of individual results by participants. All analyses will be run on the AMS, unless specified otherwise.

- Summary of ADAb status overall and by each visit separated by treatment group
- Summary of the time-point of the first occurrence of ADAb positivity during the treatment period by treatment group. A plot of the titer by time to first ADAb positivity will be prepared.
- All individual participant-level ADAb results will be listed.
- The number and percentage of participants in each of the 8 ADAb categories during the treatment period by treatment group.

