A study participant will be counted positive from the first visit at which the study participant achieved a positive ADAb sample result to the end of the treatment period, regardless of any missing/inconclusive or negative ADAb sample result.

If a study participant has only negative ADAb samples or only one missing/inconclusive sample with all other ADAb samples being negative, the study participant will be classified as negative. An exception remains for the Baseline Visit where only one sample could be available. If the sample is missing/inconclusive, then the sample will be classified as being negative for the cumulative ADAb status.

Otherwise, the study participant will be classified in the missing ADAb category.

Overall ADAb status will be derived as follows:

A study participant will be classified as:

- **Positive if the study participant has at least one positive sample up to the time point of interest (regardless of having missing/inconclusive data).**
- **Negative if the study participant has all the samples negative or only one missing/inconclusive sample with negative ADAb samples up to the timepoint of interest.**
- **Missing if the study participant has more than one missing ADAb result (or have more than one inconclusive sample) and all other available ADAb samples are negative up to the time point of interest.**

ADAb categories will be derived definitions are as follows:

- **Pre ADAb negative – treatment-emergent ADAb negative (Category 1):** Includes study participants who are anti-bimekizumab antibody negative at Baseline and anti-bimekizumab antibody negative at all sampling points during the period of interest (one post-Baseline

missing/inconclusive sample is allowed for subjects with pre- anti-bimekizumab antibody negative sample). This group also includes study participants who have a missing or inconclusive sample (either missing or inconclusive or insufficient volume) at Baseline (ie, pre-treatment) with all post-Baseline samples as ADAb negative.

- **Pre ADAb negative – treatment-emergent ADAb positive (Category 2):** Includes study participants who are ADAb negative at Baseline and ADAb positive at any sampling points post-Baseline during the period of interest. This group also includes study participants who have a missing sample (either missing or insufficient volume) at Baseline (ie, pre-treatment) with 1 or more post-Baseline samples as ADAb positive.

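### The ADAb rules in Section 9.3.2 class a Baseline-negative participant as negative when the only post-Baseline sample so far is missing or inconclusive

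*SAP*

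**What the plan says.** All the rules are in SAP Section 9.3.2. Section 13.2, Change #34, repeats them as a log entry.

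- **Schedule.** "Samples will be taken at Baseline, then at study Weeks 4, 8, 12, 16, 20, 24, 36 and 48", plus the premature-end-of-treatment and safety follow-up visits. For the placebo arm the Week 16 sample serves as Baseline, so its first post-Baseline sample is at Week 20.
- **Inconclusive.** Samples that are not positive "where the bimekizumab concentration exceeds the validated ADAb assay drug tolerance limit will be defined as inconclusive". This class is kept apart from negative.
- **Cumulative status.** With "only one missing/inconclusive sample with all other ADAb samples being negative, the study participant will be classified as negative". An exception covers the Baseline Visit: "If the sample is missing/inconclusive, then the sample will be classified as being negative for the cumulative ADAb status". Other participants without a positive sample are missing.
- **Overall status.** Negative also covers "only one missing/inconclusive sample with negative ADAb samples up to the timepoint of interest". The other side reads "Missing if the study participant has more than one missing ADAb result (or have more than one inconclusive sample"), with the remaining samples negative.
- **Category 1** (negative before and during treatment). "one post-Baseline missing/inconclusive sample is allowed for subjects with pre- anti-bimekizumab antibody negative sample". If the Baseline sample is missing or inconclusive, every post-Baseline sample must be negative.
- **Missing category.** "Includes study participants who are ADA_b negative, missing, or inconclusive at Baseline with some post-Baseline samples as missing or inconclusive", the other samples being negative.
- **Efficacy subgroup.** One missing or inconclusive sample is tolerated if the rest are negative.

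Section 10.2.2 uses Category 1 for the column of treatment-emergent adverse events in participants negative at every time point.

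**The concern.** An allowance of one non-evaluable sample is reasonable when several evaluable ones surround it. None of these rules asks for even one. At the first post-Baseline visit the allowance can use up the only post-Baseline information, and the Baseline result alone then decides a post-Baseline label. Yet the SAP defines inconclusive separately because drug above the tolerance limit prevents the assay from ruling antibodies out.

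The SAP is also uneven on this. A Baseline-positive participant with some post-Baseline samples missing or inconclusive and the others negative goes to Category 6, ADAb inconclusive. Comparable uncertainty in a Baseline-negative participant can be labelled negative.

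At stake are the by-visit status tables, the category counts, the antibody-negative efficacy subgroup and the reference column of the adverse event table. Status can also move from negative to missing at the next visit with no new laboratory finding, merely because a second sample is non-evaluable.

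**Working it through.** The SAP states no figure on this point, so the check applies each rule to each sample pattern. N is an evaluable negative, M is missing or inconclusive, and the first letter is Baseline.

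| Pattern | Cumulative | Overall | Category | Efficacy subgroup |
|---|---|---|---|---|
| N M | negative | negative | 1; also Missing (note a) | negative |
| M N | negative | negative | 1 | negative |
| M M | missing; negative if the Baseline reclassification carries forward | missing (note b) | none described | missing |
| N M M | missing | missing (note b) | Missing (note a) | missing |
| N M N or N N M | negative | negative | 1 and Missing | negative |
| N, then seven N and one M | negative | negative | 1 and Missing | negative |

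Note a: this holds if Baseline counts among the other samples in the Missing definition, which does not restrict them to post-Baseline. For N M N and N N M the overlap needs no such reading.

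Note b: one missing plus one inconclusive sample fits neither the overall negative wording nor, read literally, the overall missing wording.

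Three results follow.

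1. N M is the core problem: negative on three rules and eligible for Category 1, with no evaluable post-Baseline sample. It occurs at the first post-Baseline visit, or permanently if no further sample is taken or counted.
2. A second non-evaluable sample ends it: N M M is missing.
3. A lone M at Baseline is negative for cumulative status at the Baseline Visit. Overall status is undefined there, since that rule needs a negative sample.

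**Effect on counts (assumed rates).** Section 2.4 plans 3 × 140 = 420 participants on bimekizumab from Week 0. Suppose all are Baseline negative and a share m has a missing or inconclusive Week 4 sample. The number labelled negative at Week 4 without a post-Baseline result is 420m:

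- m = 5%: 420 × 0.05 = 21
- m = 10%: 420 × 0.10 = 42
- m = 20%: 420 × 0.20 = 84

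**Effect on a proportion positive (assumed rates).** Let p be positivity among evaluable participants and f the share of the denominator that is non-evaluable but retained as negative. Reported positivity is p(1 − f). With p = 20%:

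- f = 1%: 0.20 × 0.99 = 19.8%
- f = 5%: 0.20 × 0.95 = 19.0%
- f = 10%: 0.20 × 0.90 = 18.0%

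The relative shortfall equals f. The formula applies only where such participants stay in a denominator that otherwise excludes missing. With the whole Active Medication Set as denominator, moving someone from negative to missing leaves percent positive unchanged.

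**The case against.** The best defence is that the rules already contain most of the protection needed. Two or more missing samples give missing. Category 1 grants no further allowance when Baseline is missing. By-visit prevalence leaves missing samples out of its denominator. With eight scheduled post-Baseline samples, one gap among seven negatives is ordinary tolerance. Early leavers may also have premature-end-of-treatment and follow-up samples. The analysis is descriptive, serves an other objective, and individual results are listed.

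Much of this stands, and it rules out two stronger readings.

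- A reader might infer that participants with no evaluable sample at all are reported as negative throughout. The text says so only for cumulative status at the Baseline Visit. Whether the reclassified sample still counts as negative at Week 4 is not settled. Without that step, two missing samples give missing.
- A reader might infer a quantified understatement of immunogenicity. The SAP gives neither missing or inconclusive rates nor positivity. Missing samples are already dropped from by-visit prevalence. Inconclusive samples form a separate class that the denominator rule does not mention, so any lowering there comes from them.

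The defence does not answer the N M pattern. Followed exactly, the rules call that participant negative. Its parallel fit to the Missing category does not cure this, because the same person then has two possible classifications.

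**Conclusion.** The point holds in a limited form. The rules overstate ADAb-negative counts at the first post-Baseline visit and among participants with a single post-Baseline sample. They also allow participants with no post-Baseline evidence into the always-negative adverse event column. Category 1 and the Missing category are not mutually exclusive.

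The size cannot be derived from the document; the figures above are illustrations under assumed rates. The Week 4 effect is temporary for participants who go on to give evaluable samples. The lasting group is early leavers with one non-evaluable sample. Its size depends on whether samples not taken after discontinuation count as missing and whether follow-up samples fall in the period of interest, and the rules settle neither. If untaken samples count as missing, most early leavers become missing and the group shrinks. No efficacy test or alpha allocation is affected. The change is still worth making, because the rule as written mislabels these participants and is easy to correct.

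**What to change.** In Section 9.3.2:

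1. In the cumulative, overall, Category 1 and efficacy-subgroup rules, require at least one evaluable (negative) post-Baseline sample up to the time point before assigning post-Baseline negative. Otherwise assign missing.
2. In the cumulative rule, count a missing or inconclusive Baseline sample against the one-sample allowance at post-Baseline visits. This settles the carry-forward question. Category 1 already works this way.
3. Make Category 1 and Missing mutually exclusive, for example by limiting Missing to participants who do not meet the revised Category 1.

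Under these rules N M becomes missing, M M becomes missing without ambiguity, and N M N stays negative and in Category 1 only. The cost is a short wording change and one programming condition. The downside is that a few participants move from negative to missing.
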